#### 9.4.3 ANALYSIS OF THE SECONDARY ENDPOINT(S)

The secondary endpoint will be assessed using either Chi-square, Fisher's exact, Mann Whitney U or the best test for the data.

#### 9.4.4 SAFETY ANALYSES

N/A

#### 9.4.5 BASELINE DESCRIPTIVE STATISTICS

Demographic and pre-intervention variables will be described as following:

Categorical variables will be described using the frequency and proportions. Continuous variables will be described using median and the interquartile range (Q1, Q3). Chi-square or Fisher's test and Student's t-test or Mann-Whitney U test will be used depending on type of data.

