## 3 OBJECTIVES AND ENDPOINTS

OBJECTIVES	ENDPOINTS	JUSTIFICATION FOR ENDPOINTS	PUTATIVE MECHANISMS OF ACTION
Primary			
Do TAP blocks improve pain score?	Change in pain score for the intervention versus placebo groups.	Assessing causal effect of TAP block on pain levels through the RCT design is the gold standard approach.	
Secondary			
Do TAP blocks decrease opioid and other pain medication use after surgery?	Assessing number/volume of pain medication.	TAP blocks should directly impact pain medications usage.	
Tertiary/Exploratory			
Does TAP block usage affect complications after surgery?	Assessing complication rate differences between the intervention and placebo groups with regards to complications.	Complications can differ based on treatment. We want to assess if complications rates differ between the two groups.	

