## 4 STUDY DESIGN

### 4.1 OVERALL DESIGN

After receiving approval for the study, we will conduct a prospective single institution randomized clinical trial assessing if using a TAP block perioperatively can reduce pain scores after surgery. Other endpoints include whether there are differences in pain medication usage and complications.

Patients will be screened by research team members and attending surgeons. If the patient is interested, we will consent them for the study after they understand the study details, procedures, and expectations. We will then consent using IRB approved study consent forms and procedures. Patients will undergo a laparoscopic inguinal hernia repair according to standard procedures. Our study will assess if a TAP block impacts pain scores. Patients will be randomized to receive the intervention or placebo. Sequentially numbered sealed opaque envelopes with group allocation inside will alert the anesthesiologist/ surgeon to order Tap block composed of 0.25% bupivacaine or placebo (normal saline).

Inguinal hernia repair will be performed in standard fashion that each individual surgeon is familiar with. No additional tests or blood work outside the standard of care for IHR will be performed for research purposes. In addition, some patients will be given TAP blocks before surgery to help in pain management. In addition, patients will be discharged with a worksheet on which they are to record analgesic use and pain scores on postoperative days one, two, three and four. They are expected to bring the completed log to their two-week follow up visit with their surgeon. Patients may also expect to receive a phone call from a member of the surgical team to remind them to record these metrics.

The TAP block is done pre-procedure using 0.25% bupivacaine. If patients weigh<100 kg, they will receive a total of 50 mL (25 mL on each side of the abdominal wall). If patients weigh>100 kg, they will receive a total of 60 mL (30mL on each side of the abdominal wall). The TAP plane is identified using ultrasound. All anesthesiologists (not surgeons) working with the attendings involved in this study have been trained in this technique; it is a routine part of their practice. It is anesthesiologists who will be performing the block.

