### 9.2 SAMPLE SIZE DETERMINATION

Based on previous clinical trials using a pain medication intervention prior to surgery, our sample of 100 will be enough to detect a difference, should one exist. Moreover, the intervention and placebo will be administered randomly with an overall ratio of 1:1 to maximize power for analysis.

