### 9.4 STATISTICAL ANALYSES

#### 9.4.1 GENERAL APPROACH

For descriptive analyses categorical variables will be described using the frequency and proportions. Continuous variables will be described using median and the interquartile range (Q1, Q3). All p-values of statistical tests will be two-tailed with a  $p < 0.05$  considered statistically significant.

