#### 9.4.2 ANALYSIS OF THE PRIMARY ENDPOINT(S)

The primary endpoint of differences on pain score will be analyzed using the Wilcoxon rank sum test or Mann-Whitney U test.

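### Baseline variables are significance-tested, the primary rank-sum test is unadjusted, and the mixed model of Section 2.2 is missing from Section 9.4: a loss of efficiency, not a bias

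*Combined protocol and SAP*

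**What the plan says.** Section 9.4.5 plans frequencies and proportions, or medians and quartiles, for demographic and pre-intervention variables. It then adds that "Chi-square or Fisher's test and Student's t-test or Mann-Whitney U test will be used", according to the type of data. It names no variable. It does not state that the tests compare arms, but no other grouping is in view.

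Section 9.4.2 says that the primary endpoint will be "analyzed using the Wilcoxon rank sum test or Mann-Whitney U test". These are two names for one test, and it takes no covariates. Section 9.4 contains no stratified or adjusted analysis; ANCOVA appears only in the template list of abbreviations.

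Section 2.2 criticises earlier papers for simple tests that ignore repeated measurement, and promises mixed effects models for pain scores and opiate consumption over time. It names no baseline covariate, and Section 9.4 does not mention the model.

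Three further passages bear on possible covariates:
- Section 3 gives the primary endpoint as "Change in pain score for the intervention versus placebo groups", while Section 4.1 schedules worksheet pain scores on postoperative days 1 to 4 only.
- Section 4.1 states that "Inguinal hernia repair will be performed in standard fashion that each individual surgeon is familiar with".
- Sections 4.1 and 6.1.2 make the injected volume depend on body weight, so weight must be known before the block.

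**The concern.** A baseline significance test in a randomized trial tests a null hypothesis that randomization has already made true. Its p-value measures neither the quality of the randomization nor the prognostic importance of an imbalance. Some small p-values will appear by chance, and the plan does not say what would follow from one.

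Baseline information is useful when it enters the outcome analysis. A variable that predicts postoperative pain, fixed in advance as a covariate, removes variation from the error term and narrows the confidence interval with no extra patients. The plan tests baseline variables, where that tells it nothing, and leaves them out of the primary analysis, where they might help. The model that could hold them is promised in the background section and then dropped. At stake is some precision in a trial of 100 patients, and a clear statement of how pain scores will be analysed.

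**Working it through.** **Inputs.** Section 9.4.1: two-sided 0.05. Section 9.2: 100 patients, "administered randomly with an overall ratio of 1:1 to maximize power for analysis", hence 50 per arm. Effect size, SD and power are not given; the basis offered is "Based on previous clinical trials using a pain medication intervention prior to surgery". The covariate strength R² (share of pain-score variance explained) is also not given, so a range is assumed.

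**The plan's own figure.** The 100 cannot be reproduced without an effect size, SD or power. Inverted, 50 per arm detects (1.960 + 0.842) × √(2/50) = 0.56 SD with 80% power by a t-test. By the rank-sum test it is 0.56/√0.955 = 0.573 SD (efficiency 3/π = 0.955, normal outcomes).

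**Chance findings among baseline tests.** With m independent tests at 0.05, the chance of at least one below 0.05 is 1 − 0.95^m: 23% for m = 5, 40% for m = 10, 54% for m = 15. The value of m is assumed, as no variable is named.

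**Upper bound on the gain.** Take an effect with 80% unadjusted power, so the expected test statistic is 1.960 + 0.842 = 2.802. Adjustment multiplies the residual variance by 1 − R². Power = Φ(2.802/√(1 − R²) − 1.960), and equivalent N = 100/(1 − R²).

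| R² | Power | Equivalent N |
|---|---|---|
| 0 | 80% | 100 |
| 5% | 82% | 105 |
| 10% | 84% | 111 |
| 20% | 88% | 125 |

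**Cost of estimating the covariates.** Chance imbalance across k covariate terms inflates the variance of the arm effect by roughly 1 + k/98. With v = (1 − R²)(1 + k/98), power = Φ(2.802/√v − 1.960). The number of surgeons is not given, so k = 4 and k = 8 are assumptions.

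| R² | k = 4 | k = 8 |
|---|---|---|
| 0 | 78% | 77% |
| 5% | 80% | 79% |
| 10% | 83% | 81% |
| 20% | 87% | 85% |

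Break-even is R² = 1 − 1/(1 + k/98): 3.9% for k = 4 and 7.5% for k = 8.

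**Check by simulation.** 20,000 trials per setting, 50 per arm, normal outcomes, true difference 0.5 SD, one covariate with correlation r to the outcome:

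| r (R²) | Mann-Whitney | ANCOVA |
|---|---|---|
| 0 (0) | 67.5% | 69.4% |
| 0.1 (1%) | 67.5% | 69.6% |
| 0.3 (9%) | 67.5% | 73.4% |
| 0.5 (25%) | 68.1% | 81.6% |

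The 2-point gap at r = 0 is rank test against linear model under normality. The part due to the covariate is 73.4 − 69.4 = 4.0 points at r = 0.3 and 81.6 − 69.4 = 12.2 points at r = 0.5.

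**The case against.** The rank-sum test is valid under randomization and defensible for pain scores. Leaving out covariates is a choice about efficiency, and a reader who inferred a biased primary result would be wrong. That stands in full.

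Several stronger readings are tempting, and the documents do not support them:
- *Baseline variables are only tested.* Section 9.4.5 plans descriptive summaries first; only the added sentence on tests needs to go.
- *Recorded prognostic data are thrown away.* No variable is named for analysis or called prognostic, and no preoperative pain score is scheduled. One- versus two-sided repair is never mentioned; the documents speak only of injection on each side. Weight must be known and technique may differ by surgeon, but nothing links either to pain.
- *The trial has no power to spare.* Section 9.2 says only that "our sample of 100 will be enough to detect a difference, should one exist". For a true difference of 0.8 SD, rank-sum power is Φ(0.8 × √(50 × 0.955/2) − 1.960) = 97%, and R² = 10% adds about one point.
- *The plan will adjust after seeing baseline p-values.* No rule links those tests to any model. The plan is silent on this, and silence is not an intention.
- *82, 84 and 88% are net gains.* They take no account of covariate terms. With eight terms and R² = 5%, power falls slightly below the unadjusted figure.

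It can also be said that moving to a mixed model goes further than adding covariates. That is fair, and the figures above do not quantify the effect of repeated measurement. But Section 2.2 already promises the model, so Sections 2.2 and 9.4.2 have to be reconciled in any case.

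**Conclusion.** The point holds as a cheap improvement in efficiency and prespecification. The baseline tests are uninformative, the primary test is unadjusted, and the model promised in Section 2.2 is absent from Section 9.4. Deleting the baseline tests changes no trial result by itself; any gain comes from the adjusted model.

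The size cannot be derived from the documents. It rests on an assumed 80% starting power, an assumed R², approximately normal outcomes and no loss to follow-up. On those terms the ceiling is about 2, 4 or 8 points of power for R² of 5, 10 or 20%. The net gain is smaller and may be nil or slightly negative when the covariates are weak or the surgeon terms many. This argues for a short list with small-volume surgeons pooled.

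**What to change.** 1. Section 9.4.5: delete the sentence on tests and present the planned summaries by arm.
2. Section 9.4.2: carry forward the mixed model of Section 2.2 over postoperative days 1 to 4, and state which arm contrast is primary, for example the difference averaged over the four days. Fix the covariates before unblinding: weight, surgeon (small-volume surgeons pooled) and a preoperative pain score.
3. Add recording of that preoperative score to the procedures. Section 3 calls the endpoint a change, and no reference value is currently scheduled.
4. Add one- versus two-sided repair only if it is recorded and known before the block.
5. Keep the rank-sum test as a prespecified sensitivity analysis.

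The cost is some rewording, a few degrees of freedom and one extra recorded score. No additional patients are needed.

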#### 9.4.6 PLANNED INTERIM ANALYSES

N/A

#### 9.4.7 SUB-GROUP ANALYSES

N/A

#### 9.4.8 TABULATION OF INDIVIDUAL PARTICIPANT DATA

No individual data will be presented.

#### 9.4.9 EXPLORATORY ANALYSES

Other analyses that will occur will be compare types of complications and their rates between the intervention and placebo groups.

### 10 SUPPORTING DOCUMENTATION AND OPERATIONAL CONSIDERATIONS

#### 10.1 REGULATORY, ETHICAL, AND STUDY OVERSIGHT CONSIDERATIONS

##### 10.1.1 INFORMED CONSENT PROCESS

###### 10.1.1.1 CONSENT/ASSENT AND OTHER INFORMATIONAL DOCUMENTS PROVIDED TO PARTICIPANTS

Consent forms describing in detail the study intervention, study procedures, and risks will be given to the participant and written documentation of informed consent will be completed prior to starting the study intervention.

###### 10.1.1.2 CONSENT PROCEDURES AND DOCUMENTATION

Adults will be consented after they receive information regarding the study and express interest. All procedures will be conducted according to institutional regulations.

#### 10.1.2 STUDY DISCONTINUATION AND CLOSURE

Study discontinuation may be as a result of PI choice and or as a result of the oversight committee of the IRB.

#### 10.1.3 CONFIDENTIALITY AND PRIVACY

Data will be obtained using a patient medical record number and saved on a database to be analyzed at a later time. The research data will be stored under a random research code that will be linked to a subject's medical record number. It will be separate from the data collection sheet, which uses identifiable data. To reiterate: patient names and MRNs will not be used on this separate sheet. Each patient must be linked to their information to ensure the data is accurate and corresponds to the appropriate patient. In addition, information must be stored with identifiers in the event that an additional parameter of import is found at a later time and must be retrospectively obtained. Data will be stored on a computerized database with a unique code number not related to any subject identifiers. The link between the code and the data itself will be stored in separate locations. The code sheet will be kept on a separate password protected hard drive (another computer) that only listed investigators will have access to. Data files that are not stored on a server maintained by Mount Sinai's IT department will be encrypted. All files containing identifiers that are stored on a computer connected and managed by the Mount Sinai server will be password protected and restricted to the research team.

#### 10.1.4 FUTURE USE OF STORED SPECIMENS AND DATA

There is no future use or storage of data after completion of the study.

#### 10.1.6 SAFETY OVERSIGHT

The research team, the PI and other investigators will be responsible for oversight.

#### 10.1.7 CLINICAL MONITORING

Clinical site monitoring will be conducted to ensure that the rights and well-being of trial participants are protected, that the reported trial data are accurate, complete, and verifiable, and that the conduct

of the trial is in compliance with the currently approved protocol/amendment(s), with International Council on Harmonisation Good Clinical Practice (ICH GCP), and with applicable regulatory requirement(s).

#### 10.1.8 QUALITY ASSURANCE AND QUALITY CONTROL

Quality management will occur with oversight of the PI and other investigators. The research team with regular meetings will discuss and keep appropriate quality for the study.

#### 10.1.9 DATA HANDLING AND RECORD KEEPING

##### 10.1.9.1 DATA COLLECTION AND MANAGEMENT RESPONSIBILITIES

Data collection will be the responsibility of the research members. The investigator will be responsible for ensuring the accuracy, completeness, legibility, and timeliness of the data reported. All source documents will be completed in a neat, legible manner to ensure accurate interpretation of data. Hard copies of the study visit worksheets will be provided for use as source document worksheets for recording data for each participant consented/enrolled in the study.

##### 10.1.9.2 STUDY RECORDS RETENTION

Study records will be kept for no longer than 6 years after the study.

#### 10.1.10 PROTOCOL DEVIATIONS

All protocol deviations will be recorded and reported to IRB.

#### 10.1.11 PUBLICATION AND DATA SHARING POLICY

Data will not be shared with any other institutions or sites. All policies as required by the IRB.

#### 10.1.12 CONFLICT OF INTEREST POLICY

All conflicts of interest will be reported to the IRB and FCOI committee.

#### 10.2 ADDITIONAL CONSIDERATIONS

N/A

#### 10.3 ABBREVIATIONS AND SPECIAL TERMS

*The list below includes abbreviations utilized in this template. However, this list should be customized for each protocol (i.e., abbreviations not used should be removed and new abbreviations used should be added to this list). Special terms are those terms used in a specific way in the protocol. For instance, if the protocol has therapist-participants and patient-participants, those terms could be included here for purposes of consistency and specificity.*

AE	Adverse Event
ANCOVA	Analysis of Covariance
CFR	Code of Federal Regulations
CLIA	Clinical Laboratory Improvement Amendments
CMP	Clinical Monitoring Plan
COC	Certificate of Confidentiality
CONSORT	Consolidated Standards of Reporting Trials
CRF	Case Report Form
DCC	Data Coordinating Center
DHHS	Department of Health and Human Services
DSMB	Data Safety Monitoring Board
DRE	Disease-Related Event
EC	Ethics Committee
eCRF	Electronic Case Report Forms
FDA	Food and Drug Administration
FDAAA	Food and Drug Administration Amendments Act of 2007
FFR	Federal Financial Report
GCP	Good Clinical Practice
GLP	Good Laboratory Practices
GMP	Good Manufacturing Practices
GWAS	Genome-Wide Association Studies
HIPAA	Health Insurance Portability and Accountability Act
IB	Investigator's Brochure
ICH	International Council on Harmonisation
ICMJE	International Committee of Medical Journal Editors
IDE	Investigational Device Exemption
IND	Investigational New Drug Application
IRB	Institutional Review Board
ISM	Independent Safety Monitor
ITT	Intention-To-Treat
LSMEANS	Least-squares Means
MedDRA	Medical Dictionary for Regulatory Activities
MOP	Manual of Procedures
NCT	National Clinical Trial
NIH	National Institutes of Health
NIH IC	NIH Institute or Center
OHRP	Office for Human Research Protections
PI	Principal Investigator
QA	Quality Assurance
QC	Quality Control
SAE	Serious Adverse Event
SAP	Statistical Analysis Plan
SMC	Safety Monitoring Committee

<Protocol Title>

Protocol <#>

Version <X.X>

DD Month YYYY

SOA	Schedule of Activities
SOC	System Organ Class
SOP	Standard Operating Procedure
UP	Unanticipated Problem
US	United States

NIH Protocol Template for Behavioral and Social Sciences Research

18

Effective Date: 8/10/2022

End Date: 7/25/2023

## 10.4 PROTOCOL AMENDMENT HISTORY

The table below is intended to capture changes of IRB-approved versions of the protocol, including a description of the change and rationale. A **Summary of Changes** table for the current amendment is located in the **Protocol Title Page**.

